### 10.3.2 Adverse Events Occurring After Study Treatment

Adverse events will be collected from the time of the patient's first receipt of investigational product until the patient completes the study or terminates from the study.

Serious AEs will be collected from the time of the patient's first receipt of investigational product until the patient completes the study or terminates from the study.

### **10.3.3 Adverse Events Occurring Following Patient Discontinuation of Treatment**

For patients who prematurely discontinue study treatment (see [Section 8.3.3](#)), but who are not withdrawn from the study, AEs will continue to be recorded until the patient completes the study (see [Section 6.2.1.1](#) for definition of patient completion). See [Section 10.3.4](#) for reporting requirements after the patient completes the study.

### **10.3.4 Serious Adverse Events Occurring Following Patient Completion of the Study**

If, at any time after the patient has completed participation in the study (as defined in [Section 6.2.1.1](#)), the Investigator or study staff becomes aware of an SAE that they believe is possibly related or related to the investigational product (see [Section 10.2.1](#)), then the event and any known details should be reported promptly to the Sponsor. Follow the reporting instructions in [Section 10.5](#).

## **10.4 Recording of Adverse Events/Serious Adverse Events**

All AEs/SAEs experienced by the patient will be recorded on the eCRF. Information including a concise description of the event; date and time of event onset and resolution; determination of seriousness, severity, corrective treatment, outcome, relationship to investigational product; and action taken regarding the investigational product will be recorded. Vital signs, laboratory results, and other safety assessments noted in [Section 9.4](#) will be recorded, if they meet the definition of an AE (see [Section 10.1.1](#)). When possible, a diagnosis should be recorded as an AE, rather than symptoms or isolated laboratory abnormalities related to that diagnosis. A medical or surgical procedure is not an AE; rather the condition leading to the procedure should be recorded as the AE. If the condition is not known, the procedure must be reported as an AE instead. Similarly, death is not an AE, but is rather the outcome of the AE(s) that resulted in death. If the AE(s) leading to death are not known, then death must be reported as an AE.

All SAEs experienced by the patient will be recorded on an SAE Report Form and reported to the Sponsor according to [Section 10.5](#).

## 10.5 Reporting of Serious Adverse Events

The necessity and time requirements for reporting of SAEs to the Sponsor or its designee and/or regulatory agencies are as follows:

- All SAEs must be reported to the Sponsor's GPE Department within 1 calendar day of the Investigator's first knowledge of the event by fax or e-mail regardless of relationship to study procedures or treatment. The Investigator is requested to supply detailed information regarding the event at the time of the initial report.
- A completed Clinical Study SAE Report Form containing a detailed written description of the event along with additional supporting documents (eg, discharge letters, autopsy reports, and other documents) will be faxed to the Sponsor's GPE Department within 2 calendar days of the Investigator's first knowledge of the event. (If faxed within 1 calendar day of the Investigator's first knowledge, this form may serve as the initial notification).
- Follow-up information, which may include copies of relevant patient records and other documents not available at the time the initial SAE Report Form was completed, must be sent to the Sponsor's GPE Department as soon as available. Follow-up SAE reports may describe the evolution of the reported events and any new assessment of their outcome and/or relationship to treatment. Full supporting documentation should be solicited by the investigative site even if the SAE occurred at another institution. Such documentation may include copies of relevant patient/hospital records, and pathology or autopsy reports.
- The Sponsor's GPE Fax is available for SAE reporting on a 24-hour basis and is reviewed during normal business hours.

Genzyme Global Pharmacovigilance and Epidemiology
- [contact] - Email: [contact]

- Investigators will receive copies of expedited safety reports that the Sponsor sends to regulatory agencies. The Investigator is responsible for fulfilling local reporting requirements to their Institutional Review Board (IRB)/ Independent Ethics Committee (IEC). Investigators in the US will report events to their IRB in accordance with applicable standard operating procedures and/or local reporting requirements. In the European Union, the Sponsor will be responsible for notifying the IEC and Competent Authorities of any serious unexpected related adverse events (ie, Suspected Unexpected Serious Adverse Reaction). Investigators must forward copies of the IRB/IEC notification to the Sponsor or its designee.

## **10.6 Follow Up of Adverse Events/Serious Adverse Events**

All AEs/SAEs documented at a previous visit/contact that are designated as ongoing will be reviewed by the Investigator at subsequent visits/contacts.

The Investigator will provide follow-up information for any SAE to the Sponsor's GPE department, as soon as it is available. The Sponsor or regulatory authorities may request additional information regarding an SAE.

All AEs will be followed until resolution or study termination. Serious AEs will be followed until resolution, the condition stabilizes, or the Investigator and Sponsor agree that follow up is no longer necessary. Rules for AE/SAE follow up apply to all patients, including those withdrawn prematurely to the extent allowed by the patient's consent. The Investigator will ensure that follow up includes further investigations consistent with appropriate medical management and patient consent to elucidate the nature and/or causality of the AE/SAE.

For the purposes of the study, status of ongoing and new AEs/SAEs will be assessed 30 days after the patient's administration of investigational product. Any new AE or SAE that occurs during the 30-day follow-up period and prior to initiation of commercial therapy and is assessed as related to the drug or study procedures will be reported/collected in the clinical database. All AEs will continue to be followed until the 30-day assessment. Ongoing SAEs at the 30-day follow-up assessment will need to be further followed until resolution, until the Investigator deems follow up is no longer medically necessary or until the patient is lost to follow up. Adverse events and SAEs reported after the initiation of commercial product will be considered spontaneous reports for the purposes of regulatory reporting. Refer to the SOM for details of this assessment.

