### **8.3 Dosing Considerations**

#### **8.3.1 Dose Selection Rationale**

In preclinical studies, alglucosidase alfa effectively depleted tissue glycogen in GAA knockout mice in a dose-dependent fashion. The every other week (qow) dosing regimen is supported by separate nonclinical studies of glycogen clearance in GAA knockout mice, which demonstrated that qow dosing of 10, 20, 40 or 100 mg/kg of alglucosidase alfa was at least as effective as weekly dosing of the same total dose in terms of glycogen removal from the heart and skeletal muscle.

A range of dosing regimens from 10 mg/kg every week (qw) to 40 mg/kg qow has been used in clinical studies with alglucosidase alfa in patients with infantile- and late-onset Pompe disease.

Current human experience with alglucosidase alfa indicates that doses from 10 mg/kg qw to 40 mg/kg qow have been well tolerated. Clinically relevant responses in efficacy measurements have been observed in patients with infantile- as well as late-onset Pompe disease at all dose levels of alglucosidase used to date. In late-onset patients, alglucosidase alfa administered at a dose of 20 mg/kg qow for 78 weeks in Study AGLU02704 demonstrated stabilization of respiratory function, slowing the progressive decline that was seen in untreated patients, and improvement in distance walked as measured by the 6MWT. Furthermore, data analyses from Study AGLU01602 indicate no marked difference in several efficacy outcomes between the 2 dose arms of 20 and 40 mg/kg qow after 52 weeks of alglucosidase alfa treatment.

Based upon the nonclinical data outlined above, as well as relevant human experience with alglucosidase alfa in patients with Pompe disease to date, a single administration of the commercially approved dose of 20 mg/kg qow is expected to have a tolerable risk-benefit profile in this patient population.

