**15 APPENDICES**

## 15.1 Appendix A: Schedule(s) of Study Events

Written informed consent must be obtained prior to any protocol-required procedure.

	Screening	Treatment	Follow Up a
	Visit 1	Visit 2	Call
	(2 days to 4 weeks)	Day 1	Week 4 (≥30 days)
Obtain Informed Consent	X		
Confirm Study Eligibility	X	X	
Demographics, Baseline Characteristics, Medical/Surgical History and Pompe Disease History	X		
Urine Pregnancy Test b	X		
Physical Examination	X		
Weight	X		
Electrocardiogram (ECG)		X	
Serum Chemistry, Hematology, and Urinalysis	X		
IgG and Inhibitory/Neutralizing Antibodies in IgG Positive Patients		X	
Pharmacokinetic Sampling		X c	
Vital Signs		X d	
Infusion		X	
AE Assessment	Continuous Monitoring		
Concomitant Medications/Therapies	Continuous Monitoring		
a The follow-up call represents the last contact for the patient to conduct safety follow up and should occur at least 30 days after the patient's administration of investigational product.			
b For female patients of child bearing potential only.			
c Pharmacokinetic sampling schedule: pre-dose (prior to infusion); immediately (within a few minutes) before the infusion rate changes from 1 to 3 mg/kg/hr, from 3 to 5 mg/kg/hr, and from 5 to 7 mg/kg/hr; immediately before the end of infusion; and at 1, 2, 4, 8, 12, and 24 hours after end of infusion. In case of IAR, IAR(s) should be appropriately managed and PK sample has to be collected before any first time increase in infusion rate from 1 to 3 mg/kg/hr, from 3 to 5 mg/kg/hr, and from 5 to 7 mg/kg/hr achieved during administration of the remaining dose, immediately before the end of infusion; and at 1, 2, 4, 8, 12, and 24 hours after end of infusion.			
d Vital signs (blood pressure, heart rate, respiratory rate, and temperature) will be taken immediately prior to infusion and immediately prior to any infusion rate change, as well as after completion of the post-infusion observation period.			

# MSC12790 Amended Protocol 03

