### *Observation period*

The observation period will be divided into 2 epochs:

- The **prior treatment** epoch is defined as the time from the signed informed consent date up to IMP administration.
- The **after treatment** epoch is defined as the time from the IMP administration to study completion or termination.

The on-study observation period is defined as the time from start of treatment until the end of the study (defined as last protocol planned visit or the resolution/stabilization of all serious adverse events and adverse events with prespecified monitoring).

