#### **2.1.4.1 Adverse events variables**

##### ***Adverse event observation period***

- Pretreatment adverse events are adverse events that developed or worsened or became serious from the signed informed consent date up to first administration of IMP.
- Treatment-emergent adverse events are adverse events that developed or worsened or became serious after treatment.

All adverse events (including serious adverse events and adverse events with prespecified monitoring) will be coded to a preferred term (PT), and associated primary system organ class (SOC) using the version of Medical Dictionary for Regulatory Activities (MedDRA) currently in effect at Sanofi at the time of database lock.

The occurrence of adverse events (including serious adverse events and adverse events with prespecified monitoring) is recorded from the time of signed informed consent until the end of the study. Information including a concise description of the event: date and time of event onset and date and time of resolution, determination of seriousness (Yes, No), determination of IAR (Yes, No), severity (Mild, Moderate, Severe), outcome (Fatal, Not Recovered/Not Resolved, Recovering/Resolving, Recovered/Resolved, Recovered with Sequelae/Resolved with Sequelae, Unknown), relationship to treatment (Not Related, Unlikely Related, Possibly Related, Related), action taken regarding treatment (Dose Increased, Dose Not Changed, Dose Reduced, Drug Interrupted, Drug Withdrawn, Not Applicable, Unknown), and other action taken (None, Medication, Non-drug therapy, Hospitalized) is recorded.

Due to the medical significance of any new ventilator use in this patient population, any new use of invasive ventilatory support (not including planned surgical procedures, if total duration of ventilatory support is less than 3 days) will be considered an important medical event and will be reported as an SAE. If a patient requiring ventilatory support becomes ventilator independent, the next instance of invasive ventilatory support (if applicable) will be considered a new SAE.

IARs are defined as adverse events that occur during either the infusion or the observation period following the infusion which are deemed to be related or possibly related to study drug. At the discretion of the Investigator, adverse events occurring after completion of the post-infusion observation period that are assessed as related may also be considered IARs.

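### Protocol 10.6 divides events around commercial dosing by onset for the database but by report date for regulators, and the SAP makes no division, so some events are classified two ways

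*Protocol*

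**What the plan says.** **Collection.** The opening of Protocol Section 10 collects related AEs and SAEs over the 30 days after treatment and does not mention commercial product. Section 10.3.2 collects all AEs and SAEs until the patient completes or leaves the study, again without such a limit. Section 6.2.1.1 places completion at the follow-up call. Section 10.6 is narrower. It takes into the clinical database "Any new AE or SAE that occurs during the 30-day follow-up period and prior to initiation of commercial therapy", provided the event is assessed as related to the drug or study procedures.

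**Reporting.** Section 10.5 sends every SAE to the sponsor's pharmacovigilance department within 1 calendar day of the investigator's first knowledge, "by fax or e-mail regardless of relationship to study procedures or treatment". Section 10.6 then adds: "Adverse events and SAEs reported after the initiation of commercial product will be considered spontaneous reports for the purposes of regulatory reporting".

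**Timing.** Appendix A schedules one contact after Visit 2, at 30 days or later: "The follow-up call represents the last contact for the patient to conduct safety follow up". Section 8.3.1 describes the study treatment as "a single administration of the commercially approved dose of 20 mg/kg qow".

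**Analysis.** In SAP 2.1.4 the after-treatment "epoch is defined as the time from the IMP administration to study completion or termination". SAP 2.1.4.1 says: "Treatment-emergent adverse events are adverse events that developed or worsened or became serious after treatment". Neither mentions commercial dosing.

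**The concern.** Two sentences of Section 10.6 draw the line at the start of commercial product, but one uses the date the event began and the other the date it was reported. They give different answers for an event that begins before the restart and is disclosed after it. The only scheduled safety contact after Visit 2 may well fall after the restart, so this combination is a realistic one.

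The remaining sections and the SAP draw no line there. An event that begins after a non-study infusion is therefore in or out of the data depending on which section a site follows. If it is in, the SAP attaches it to the study infusion by timing alone. What is at stake is a consistent regulatory status for serious events and a clear meaning for the treatment-emergent tables.

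**Working it through.** The plan gives no figure to reproduce. The check is a comparison of sections plus date arithmetic.

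**Step 1: can a restart precede the call?** Section 10.6 itself allows for it, because its limit "occurs during the 30-day follow-up period and prior to initiation of commercial therapy" has no effect unless commercial dosing can begin inside the 30 days. Patients already treated for at least 6 months are eligible (Section 7.1), and Section 4.2 places the drug within standard care. However, no document fixes a restart date, and SAP 2.1.9 leaves later treatment to the healthcare provider.

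**Step 2: apply each rule to two events in a patient who restarts before the call.**

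| Rule | A: SAE with onset on Day 5, before restart, first mentioned at the call | B: event with onset after restart |
|---|---|---|
| Section 10, opening | collected if related | collected if related |
| Section 10.3.2 | collected | collected |
| Sections 10.4 and 10.5 | SAE form; sponsor told within 1 calendar day | same, if serious |
| Section 10.6, onset sentence | collected if related | not collected |
| Section 10.6, report-date sentence | spontaneous report for regulatory reporting | spontaneous report for regulatory reporting |
| SAP 2.1.4 and 2.1.4.1 | treatment-emergent | treatment-emergent if collected, no flag |

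Event A has two statuses. It is a study SAE under 10.3.2, 10.4 and 10.5, because the patient completes only when the call has taken place, yet 10.6 gives it the spontaneous label. For event B the two sentences of 10.6 agree with each other, but they conflict with 10.3.2, with Section 10 if the event is related, and with the SAP. An event that begins and is reported before the restart meets no conflict from the commercial cut.

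**Step 3: how much follow-up is exposed?** Let r be the days from the study infusion to the restart. Days after restart within the 30-day period = 30 − r; share = (30 − r)/30. Each r is an assumption.

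| r (days) | 30 − r | Share of 30 days |
|---|---|---|
| 7 | 23 | 77% |
| 14 (about Day 15, every-other-week interval kept) | 16 | 53% |
| 21 | 9 | 30% |
| 28 | 2 | 7% |
| after the call | 0 | 0% |

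With r = 14, a second commercial infusion falls at about 28 days, also before the call. These shares describe the onset window for event B. The window for event A is the r days before the restart.

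**Step 4: effect on a table.** With about 20 patients, one patient with a type B event moves an incidence by 1/20 = 5 percentage points, or by 1/10 = 10 points within one age group if the table is split that way.

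**The case against.** The strongest reply is that the two sentences of 10.6 do different jobs. One governs the database, and the other is limited to regulatory reporting. That is correct: they are misaligned rather than flatly contradictory.

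A reader might infer that a serious reaction to the study infusion could bypass causality assessment, SUSAR handling or ethics-committee notice. The documents do not support this. Section 10.2.1 requires a relationship for every recorded event. Sections 10.4 and 10.5 require the SAE form and the 1-day report. Section 10.5 assigns ethics-committee and EU SUSAR notification with no exception for commercial dosing. Section 10.3.4 covers SAEs thought related or possibly related even after completion. The event is labelled twice, not missed.

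A reader might also infer that every AE after a commercial infusion enters the tables as if the study infusion had caused it. That goes too far. Treatment-emergent is a class based on timing, Protocol 12.8.3 tabulates by relationship, and Sections 10 and 10.6 both restrict what is collected after Visit 2. Relationship alone will not settle the matter, though, since both infusions are alglucosidase alfa.

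Three further points carry some weight. Appendix A specifies continuous AE monitoring, so events may be disclosed before the call. Section 10.6 refers to the Study Operations Manual, which is not available here and may hold a working rule. Section 6.1.2 says routine safety assessments are not endpoints. These reduce the likelihood and the weight of the problem. They do not make the sections agree.

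**Conclusion.** The point holds as an inconsistency in date basis. Followed as written, the protocol gives one pre-restart SAE two statuses. It also gives contradictory instructions on collecting post-restart events, and the SAP would count any that are collected as emergent to the single study infusion, unmarked.

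The size depends on an unstated restart date: 0% to 77% of the 30 follow-up days over the range shown, and 53% if the every-other-week interval is kept. It would be wrong to conclude that every patient who resumes treatment is affected. A patient must restart before the call and have an event. For the double label, the event must also have begun before the restart and gone unreported until after it.

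The PK objectives are untouched. This is a modest defect in stated rules, and it is worth correcting because the correction is cheap.

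**What to change.** Use one basis throughout: onset relative to the first alglucosidase alfa infusion after the study infusion.

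- **Protocol 10.6.** Replace the report-date condition for spontaneous reports with: *with onset after the start of the first commercial infusion following the study infusion*. Add that events with earlier onset follow Section 10.5 whenever they are reported.
- **Protocol 10 (opening), 10.3.2 and 10.5.** Reconcile these with 10.6, so that all four say the same about collecting and reporting events that begin after that infusion. Changing 10.6 alone would leave the type B conflict in place.
- **Data capture.** Make sure the date and time of that infusion are recorded. The Concomitant Medication eCRF (Section 8.4) may suffice. However, SAP 2.1.2 leaves out medications started in a post-treatment period that SAP 2.1.4 does not define, so confirm this or add a field.
- **SAP 2.1.4 and 2.1.4.1.** Flag events with onset after that infusion and show them separately from the treatment-emergent events of the study infusion.

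The cost is wording in a few protocol sections and one part of the SAP, and at most one eCRF field. The drawback is a shorter treatment-emergent window for patients who restart early, about 14 days if the every-other-week interval is kept. The report should state this.

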## **10.7 Pregnancy Reporting**

Female patients will be instructed to notify the Investigator immediately if they discover they are pregnant. Pregnant female patients will be discontinued from the study. Investigators are encouraged to enroll pregnant patients in the Pompe Registry.

Male patients will be instructed to notify the Investigator immediately if they discover that their sexual partner is pregnant.

If the Investigator learns of a report of pregnancy at any time after signing the informed consent, the Investigator should follow the instructions in [Section 10.5](#) to contact GPE within 24 hours; however, the Investigator will be asked to complete the Pregnancy forms rather than SAE forms, because healthy pregnancy is not an AE. The patient will be followed until the outcome of the pregnancy is known (eg, live birth or stillbirth). The Investigator will be responsible for this follow up.

If not otherwise established, the Investigator will inform the patient that the Sponsor is required to gather information regarding the course and outcome of the pregnancy after exposure to a study product. The progress of the pregnancy must be followed until the outcome of the pregnancy is known (i.e., delivery, elective termination, or spontaneous abortion). If the pregnancy results in the birth of a child, additional follow-up information may be requested.

The Investigator will be asked to obtain follow-up information no later than 2 months after the gestational period to obtain maternal/fetal/neonatal outcome and any other relevant information.

Follow-up information may be requested at additional timepoints. All study related visits/contacts involving a known pregnancy should include pregnancy status assessment until pregnancy outcome is known.

Please note that pregnancy in and of itself is not an AE or an SAE. Pregnancy should not be entered into the CRF as an AE unless the Investigator suspects an interaction between the study treatment and the contraceptive method. Additionally all information received will be assessed for any AEs and SAEs and processed per study guidelines. If the patient is discontinued because of pregnancy, pregnancy will be documented as the reason for study discontinuation. Spontaneous abortions and stillbirths are reported as SAEs.

